4.4.1 Criteria for Early Study Termination

There are no prespecified criteria for terminating the study early.

5 Study Population

Healthy Japanese male participants between the ages of 20 and 45 will be enrolled in this study.

Prospective approval of protocol deviations related to inclusion criteria (e.g., waivers or exemptions) is not permitted.

5.1 Inclusion Criteria

Participants are eligible to be included in the study only if all of the following criteria apply:

Post-marketing Clinical Study Protocol Number-Version Number: 851-00

Type of participant/target disease

1) Is a Japanese male between the ages of 20 and 45 at the time of signing informed consent.

Participant Demographics

2) Has a Body Mass Index (BMI)[†] between 18.5 kg/m² and 32.0 kg/m² at the time of screening test.

 † BMI = weight (kg)/height (m)²

Note: BMI values will be rounded to one decimal place.

Informed Consent

3) Has understood the methodology of the study and voluntarily signed written informed consent to study participation.

Others

- 4) Is considered to be in good health by an investigator based on the medical history, physical findings, vital signs, and the results of 12-lead ECG noted at the screening test and before study drug administration. Refer to Appendix 5 for criteria for ECG abnormalities.
- 5) Is considered to be in good health based on the results of laboratory tests performed at the screening test and before study drug administration. A list of laboratory tests performed for this study is attached in Appendix 3. Refer to Appendix 6: Algorithm for Assessing Abnormal Laboratory Values for algorithm related to the assessment of abnormal laboratory values.
- 6) Has been a nonsmoker and has not used nicotine-containing products for over 3 months at the time of screening test.
- 7) Is willing to comply with the study restrictions (refer to Section 5.3 for a summary of study restrictions).

5.2 Exclusion criteria

Participants are excluded from the study if any of the following criteria apply:

Medical History

- Have a history of clinically significant endocrine, gastrointestinal, cardiovascular, hematological, hepatic, immunological, renal, respiratory, genitourinary, or neurological (including cerebrovascular stroke and epilepsy) abnormalities or diseases.
- 2) Has significant emotional problem at the time of screening test or suspected to occur during the conduct of the study, or has a history of clinically significant psychiatric disorder within the last 5 years.
- 3) Has a history of malignancy.
- 4) Has a history of clinically significant allergies to multiple antigens or severe allergies (e.g., food, drug, and latex [natural rubber] allergies), or has had an

Post-marketing Clinical Study Protocol Number-Version Number: 851-00

- anaphylactic reaction or significant intolerability (e.g., systemic allergic reaction) to prescription or non-prescription drugs or food.
- 5) Is positive for hepatitis B virus surface antigen, hepatitis C virus antibodies, syphilis, or HIV antigen or antibody on the screening test.
- 6) Had surgery, donated or lost blood within 4 weeks prior to the screening test.

Prior and Concomitant Medications

7) Requires the use or anticipates the required use of prescription or non-prescription drugs or herbal products beginning 14 days prior to study drug administration through the post-study examination (or cytochrome P450 [CYP], uridine diphosphate [UDP] glucuronic acid transferase, and/or P-glycoprotein [P-gp] inducers including St. John's wort beginning 28 days prior to study drug administration through the post-study examination). There may be certain medications that are permitted (see Section 6.4).

Prior Study (Clinical Trial) Experience

8) Has participated in another study (clinical trial) within 4 months prior to the screening test. The interval between studies (clinical trials) will be derived from the last procedure (e.g., post-study examination, follow-up of adverse events) for the last study (clinical trial) to the screening test for this study.

Diagnostic Assessments

9) Has a systolic blood pressure < 90 mmHg or > 140 mmHg, or a diastolic blood pressure < 50 mmHg or > 90 mmHg on the screening test or predose blood pressure measurement. Blood pressure measurements will be performed after maintaining a supine or semirecumbent position for at least 10 minutes.

Others

- 10) Consumes greater than 3 glasses of alcoholic beverages (definition of 1 glass: 354 mL for beer, 118 mL for wine, 29.5 mL for distilled spirits) per day.
- 11) Consumes greater than 6 servings (definition of 1 serving: equivalent to 120 mg of caffeine) of coffee, tea, cola, energy drinks, or other caffeinated beverages per day.
- 12) Is a regular user of cannabis, any illicit drugs, or has a history of drug or alcohol abuse within 2 years at the time of the screening test. Participants must have a negative predose urine drug screen.
- 13) Is unable to consent to refrain from the consumption of citrus beverages and foods (e.g., grapefruits) beginning 2 weeks prior to administration of the study drug until the end of post-study examination, and the consumption of all fruit beverages and foods for 24 hours predose and postdose.
- 14) Is or has an immediate family member (e.g., spouse, parent/legal guardian, sibling, or child) who is study site or Sponsor staff directly involved with this study.

Post-marketing Clinical Study Protocol Number-Version Number: 851-00

5.3 Lifestyle Considerations

5.3.1 Dietary Restrictions

5.3.1.1 Meals

Fasting requirements for study procedures, such as laboratory tests are specified in Section 8.

Participants will fast from all food and drinks, except water, for at least 8 hours prior to study drug administration. Participants will fast from all food and drinks except water between study drug administration and the first scheduled meal. Meals will be provided at time points specified in the study schedule. Between these meals, participants will fast from all food and drinks except water. After the 24-hour postdose tests and observations have been completed, subsequent meals and snacks will be unrestricted in caloric content, composition and timing.

Water will be provided at the time of study drug administration. Water will be restricted 1 hour prior to and 1 hour after study drug administration.

The study drug will be taken with approximately 240 mL (± approximately 10 mL) of water.

5.3.1.2 Fruit Juice

Participants will refrain from the consumption of citrus beverages and foods (e.g., grapefruits) beginning approximately 2 weeks until the post-study examination.

Participants will also refrain from the consumption of all fruit beverages and food beginning 24 hours prior to study drug administration until 24 hours after the administration. At all other times, the consumption of fruits beverages and foods (excluding citrus [e.g., grapefruits] beverages and foods) is allowed.

5.3.2 Caffeine, Alcohol, and Tobacco Restrictions

5.3.2.1 Caffeine

Participants will refrain from the consumption of caffeinated beverages and xanthine-containing products for 12 hours prior to the screening test and 12 hours prior to post-study examination, and beginning 12 hours prior to study drug administration until 12 hours after the administration. At all other times, caffeinated beverages and xanthine-containing products will be limited to no more than 6 units per day (definition of 1 unit: equivalent to 120 mg of caffeine).

5.3.2.2 Alcohol

Participants will refrain from the consumption of alcohol beginning 24 hours prior to study drug administration until 24 hours after the administration. Participants will also

Post-marketing Clinical Study Protocol Number-Version Number: 851-00

refrain from the consumption of alcohol for 24 hours prior to the screening test and 24 hours prior to post-study examination. At all other times, alcohol beverages are allowed but limited to no more than 3 glasses per day (definition of 1 glass: 354 mL for beer, 118 mL for wine, 29.5 mL for distilled spirits).

5.3.2.3 Tobacco

Smoking (and the use of nicotine and nicotine-containing products) is not permitted from the screening test through the post-study examination.

5.3.3 Daily Living Activities

Participants are instructed to avoid strenuous physical activities (e.g., excessive weight lifting, running, bicycling) from the screening test through the post-study examination.

5.4 Screen failures

Screen failures are defined as participants who have consent to participate in this study but are not subsequently enrolled in the study. A minimal set of information will be collected on screen failures as well. Minimal information includes the following information specified in the "Data Handling Guidelines": participant demography, details of the reasons for screen failures, inclusion/exclusion criteria, and adverse events/serious adverse events meeting reporting requirements.

5.5 Criteria Related to Participant Replacement

If a participant withdraws from the study, a new participant (reserve participant) can participate in the study if deemed appropriate by an investigator and Sponsor. The new participant will be assigned a unique treatment/randomization number. The study site will contact the Sponsor for the new participant's treatment/randomization number.

6 Intervention in the Study

An intervention in the study is defined as the use of any study drug, marketed product or medical device in accordance with the protocol.

6.1 Dosage Schedule of the Study Drug

Table 1 shows the study drug for this study.

Post-marketing Clinical Study Protocol Number-Version Number: 851-00

Table 1 Study Drug

| Treatment Group | Type of Group | Drug Name | Туре | Dosage Form | Strength | Dose | Route | Regimen | Use | IMP/ NIMP | Supply |
|--------------------|-------------------------|---------------------------|------|----------------|----------|--------------------------|-------|-------------------|-------------------------|--------------|------------------|
| | Investigational product | ISENTRESS® Tablets 600 mg | Drug | Tablet | 600 mg | 2 tablets (1200 mg) once | Oral | Single- dosing | Investigational product | NIMP | Marketed product |

The definitions of Investigational Medicinal Product (IMP) and Non-Investigational Medicinal Product (NIMP) will be in accordance with the guidance issued by the European Commission.

The definitions of IMP/NIMP may vary with countries and regions. In such cases, applicable local laws and regulations will be followed.

Post-marketing Clinical Study Protocol Number-Version Number: 851-00

As study drug shown in Table 1, the marketed product (ISENTRESS® Tablets 600 mg) will be purchased by the study site and used for the study.

Refer to Section 8.1.8 for the details of study drug administration.

6.2 Preparation/Handling/Storage/Accountability of the Study Drug

6.2.1 Preparation of the Study Drug

There are no specific calculations or evaluations required to be performed in order to determine the dose to each participant for this study. The rationale for selection of the dose of the study drug is provided in Section 4.3.

6.2.2 Handling, Storage, and Accountability of the Study Drug

Refer to the package insert and Pharmaceutical Interview Form of ISENTRESS® Tablets 600 mg for the handling/storage/accountability of the study drug.

Only authorized site staff may administer the study drug. Only participants enrolled in the study will receive study drug administration. All study drugs will be stored in a secure, manually or automatically monitored and controlled area in accordance with the labeled storage conditions with access limited to the investigator and authorized site staff.

The study drug storage manager will be responsible for study drug accountability, reconciliation, and record keeping (i.e., receipt, reconciliation, and final disposition records).

Where study drug disposition at the site is appropriate, the study drug storage manager will ensure that disposition procedure is documented.

For the marketed products purchased for this study by the study site, the study site will record the lot numbers, the manufacturers, and expiry dates in accordance with local guidelines unless otherwise instructed by the Sponsor.

The study drug storage manager is responsible for appropriate recording, appropriate supply, storage, handling, distribution, and use of the study drug in accordance with the protocol and applicable laws and regulations, and will take all measures required.

6.3 Method to Minimize Bias: Randomization and Blinding

6.3.1 Assignment Procedure

Participants will be allocated to the treatment group by nonrandom assignment in this study.

6.3.2 Stratification

No stratification based on age, gender, or other factors will be performed.

Post-marketing Clinical Study Protocol Number-Version Number: 851-00

6.3.3 Blinding

This is an open-label study; therefore, the treatment detail is open to the investigator, participants, and the Sponsor.

6.4 Concomitant Therapy

Even if a participant does not discontinue prior medications for 14 days prior to study drug administration (or CYP, UDP glucuronic acid transferase, and/or P-gp inducers including St. John's wort for 28 days prior to study drug administration), he may be included in the study if the investigator can rationalize that the use of the prior medication(s) has no clinically significant effect on the study.

Concurrent use of any medication prescribed or obtained during the study period, or concurrent vaccination must be discussed between the investigator and Sponsor prior to administration, unless treatment needs to be started before their discussion. The participant will be allowed to continue in the study if both the Sponsor and the investigator agree.

6.4.1 Rescue and Supportive Therapies

No rescue or supportive therapies are specified for this study.

6.5 Dose Modification for the Study Drug (Titration/Adjustment/Other)

No dose modification is specified for this study.

6.6 Intervention After the End of the Study

There is no intervention specified to be performed after the end of this study.

6.7 Disclosure of Treatment Assignments

This is an open-label study; therefore, the participants, the study site personnel, the Sponsor, or its delegate are not blinded. The drug information (name, strength, or potency) is included in the package insert, and no emergency key containing treatment assignments will be provided.

7 Discontinuation of Study Drug Administration and Participant Withdrawal From the Study

7.1 Discontinuation of Study Drug Administration

Participants may discontinue study drug administration at any time for any reason or be discontinued from the administration at the discretion of the investigator should any untoward event occurs. In addition, a participant may be discontinued from study drug

Post-marketing Clinical Study Protocol Number-Version Number: 851-00

administration by the investigator or the Sponsor if study drug administration is inappropriate, the protocol is violated, or for administrative or other safety reasons. Specific procedures to be performed at the time of discontinuation of study drug administration are provided in Section 8.1.9.

7.2 Participant Withdrawal From the Study

A participant must be withdrawn from the study if the participant or his legally acceptable representative withdraws consent.

If a participant withdraws from the study, they will no longer receive study drug administration or be followed at protocol-specified visits.

Specific procedures to be performed at the time of withdrawal from the study are provided in Section 8.1.9. The procedures to be performed should a participant repeatedly fail to return for protocol-specified visits and/or if the study site is unable to contact the participant are specified in Section 7.3.

7.3 Lost to Follow-up

If a participant fails to return to the study site for a specified study visit or if the site is unable to contact the participant, the following procedures will be performed.

- The site must attempt to contact the participant and reschedule the missed visit. If the participant is contacted, the participant will be explained about the importance of maintaining the protocol-specified visit schedule.
- The investigator or designee must make every effort to regain contact with the participant at each missed visit (e.g., telephone calls and/or a certified letter to the participant's last known mailing address or equivalent methods). These contact attempts will be documented in the participant's medical record.
- Note: A participant is not considered lost to follow-up until the last scheduled visit for the individual participant. The missing data for the participant will be handled in accordance with the prespecified statistical data handling and analysis guidelines.

8 Study Assessments and Procedures

- Study procedures and their timing are outlined in "1.3 Study Schedule."
- Adherence to the protocol-specified requirements, including those specified in "1.3 Study Schedule," is essential and required for study conduct.
- The principal investigator is responsible for ensuring that the study procedures are conducted by appropriately qualified or trained staff. Delegation of study site personnel responsibilities will be documented and stored in the Investigator Study File Binder (or equivalent).
- Study-related medical (or dental) decisions will be made by an investigator who is a qualified physician (or dentist only when appropriate).

Post-marketing Clinical Study Protocol Number-Version Number: 851-00

- The investigator must perform and evaluate all screening items to confirm that potential participants meet all inclusion criteria. The investigator will record the details of all participants screened, and manage the records of confirming their eligibility or reasons for screening failures, as applicable.
- Procedures conducted as part of the participant's routine clinical care (e.g., hematology) before signing informed consent may be utilized for screening or baseline evaluations provided the procedure met the protocol-specified criteria and were performed within the time frame specified in "1.3 Study Schedule."
- Additional evaluations/testing may be deemed necessary by the investigator and/or the Sponsor for reasons related to participant safety. In some cases, such evaluations/testing may be potentially sensitive in nature (e.g., HIV infection, hepatitis C), and thus local laws and/or regulations may require that additional informed consent be obtained from the participant. In these cases, such additional evaluations/testing will be performed in accordance with those local laws and/or regulations.

The amount of blood collected from each participant over the duration of the study will amount to approximately 73 mL.

Repeat or unscheduled blood samples may be taken for safety reasons or for technical issues with the samples.

| Sample | Blood collected per time (mL) | Number of blood collections | Total amount of blood collected (mL) |
|---|-------------------------------|-----------------------------|--------------------------------------|
| Laboratory tests | 7 | 3 | 21 |
| Samples for the measurement of MK-0518 concentrations | 4 | 13 | 52 |
| Total amount of blood collected per participant | | | 73 mL |

8.1 Study Administrative Procedures

8.1.1 Informed Consent and Information

The investigator will obtain written consent from each participant or his legally acceptable representative prior to participating in the study. If there are changes to the participant's status during the study period (e.g., health condition or age category), the investigator will ensure the appropriate consent has been obtained.

8.1.1.1 Informed Consent and Information Related to Participating in This Study

Consent to participation in the study must be documented by the participant's dated signature or by his legally acceptable representative's dated signature on a consent form along with the dated signature of the person conducting the consent discussion.

Post-marketing Clinical Study Protocol Number-Version Number: 851-00

A copy of the signed and dated consent form will be given to the participant before participation in the study.

The initial ICF, any subsequent revised ICF, and any written information provided to the participant must receive the IRB/IEC's approval in advance of use. The participant or his legally acceptable representative will be informed immediately if new information becomes available that may affect the participant's willingness to continue participation in the study. The communication of the new information will be provided via a revised ICF or an addendum to the original consent form that captures the participant's dated signature or his legally acceptable representative's dated signature.

Information about the study and the study population will be added to the ICF template at the protocol level.

The ICF will fulfill IRB/IEC requirements, applicable laws and regulations, and the Sponsor requirements.

8.1.2 Inclusion/Exclusion Criteria

All inclusion and exclusion criteria will be reviewed by the investigator to ensure that the participant qualifies for study participation.

8.1.3 Study Identification Card

All participants will be given a study identification card identifying them as a participant in the study. The card will contain study site contact information (including telephone numbers) that can be used in the event of an emergency. The investigator or qualified designee will provide the participant with a study identification card immediately after the participant provides written consent to study participation. At the time of the provision of the participant's treatment/randomization number, the number will be added to his study identification card.

The study identification card also contains contact information for the MSD K.K. Clinical Study Emergency Center so that a health care provider can obtain information about the participant's study drug in emergency situations where the investigator is not available.

8.1.4 Medical History

Medical history will be reviewed by the investigator.

8.1.5 Prior and Concomitant Medications Review

8.1.5.1 Prior Medications

There are no planned medications other than the study drug in this study. Participants are not permitted to use prescription or non-prescription drugs or herbal products beginning 14 days prior to study drug administration through the end of post-study examination.

Post-marketing Clinical Study Protocol Number-Version Number: 851-00

Participants are not permitted to use CYP, UDP glucuronic acid transferase, or P-gp inducers including St. John's wort beginning 28 days prior to study drug administration through the post-study examination.

The investigator will review the presence or absence of prior medication use, including any protocol-specified washout requirement, and record prior medications used by the participant within 14 days prior to study drug administration.

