|------------------|--------------------------------|----------------|--------------|---|-----|---|-----|----------|---------|---------|----------|------|----|----|----------|------------------|--|
| Activities | Screening test [†] | | Pre- dose | 0 | 0.5 | 1 | 1.5 | 2 | 3 | 4 | 6 | 8 | 12 | 16 | 24 | 48 ^{§§} | study Examina- tion [‡] |
| Visit Number | 1 | 2 Admission | | | | | | | | | | | | | | Dis- charge | 3 |
| Scheduled Visits | Day -21 to Day -1 | Day -1 | Day 0 | | | | | | | | | | | | Day 1 | Day 2 | Day 10 to Day 14 |

- † Screening test will be performed within 3 weeks prior to study drug administration.
- post-study examination will be performed between Days 10 and 14 after study drug administration in each participant. However, adverse events will be examined until Day 14 study drug administration.
- § Written informed consent will be obtained before starting any study procedure.
- Predose laboratory tests will be performed within 24 hours prior to study drug administration.
- Participants will be provided with lunch after blood sampling performed 4 hours after study drug administration. The timing and content of subsequent meals will be determined by the principal investigator. All participants are provided with meals of the same content.
- # Measurements will be performed after maintaining participants in a supine or semirecumbent position for at least 10 minutes.
- †† Participants will be fasted for more than 8 hours before blood sampling for laboratory tests (hematology, clinical chemistry, and urinalysis).
- Participants will be fasted for more than 8 hours before study drug administration and for more than 4 hours after the administration. In addition, they are not permitted to drink water for 1 hour before and 1 hour after the administration.
- §§ An investigator will confirm the absence of any abnormalities in tests and examinations performed before 48 hours after study drug administration in individual participants to discharge them.

Post-marketing Clinical Study Protocol Number-Version Number: 851-00

2 Introduction

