8.1.5.2 Concomitant Medications

There are no planned medications other than the study drug in this study.

The use of all medications other than the study drug will be discussed with the Sponsor prior to administration, unless emergency treatment is necessary.

The investigator will record medication used by participants during the study.

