9.2.3 Analysis Populations

This section defines analysis populations. Data for all participants will be analyzed based on the treatment group in which individual participants have received administration.

All Subjects as Treated (AST): The set of all participants who have received at least 1 dose of the study drug, to be used for safety and tolerability evaluations.

Per-Protocol (PP): A subset of participants meeting the protocol criteria likely to provide data that sufficiently reflect efficacy under the scientific model. Protocol adherence will be determined by measures such as the exposure to study drug, the availability of measurements, and the absence of significant protocol deviations. Significant protocol deviations will be identified by the personnel involved in the collection, analysis, and interpretation of data. The data of all participants excluded from analysis will be identified and documented in the clinical study report along with the reasons for exclusion. This set of participants will be included in the pharmacokinetic analysis.

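### Does recording prior medication for only 14 days, when inducers are barred for 28, undermine the PK analysis?

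*Combined protocol and SAP*

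**What the plan says.** Section 8.1.5.1 (Prior Medications) sets two prohibition periods. Drugs and herbal products in general are barred from 14 days before dosing. Inducers of CYP, of the glucuronidating enzyme or of P-gp have a longer period, which for St. John's "wort beginning 28 days prior to study drug administration through the post-study examination" is the same as for the rest of the class. Exclusion criterion 7 (Section 5.2) repeats both periods and points to Section 6.4 for permitted medications.

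One sentence in 8.1.5.1 then sets two duties. The first is a review: "The investigator will review the presence or absence of prior medication use, including any protocol-specified washout requirement". The second is to "record prior medications used by the participant within 14 days prior to study drug administration". The review follows whichever washout applies; the recording duty is 14 days for every drug.

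Section 6.4 allows an exception for a man who did not complete either washout: "he may be included in the study if the investigator can rationalize that the use of the prior medication(s) has no clinically significant effect", and the sentence goes on to make the study the reference for that judgement. Consultation with the Sponsor is required for medication obtained during the study, and "concurrent vaccination must be discussed between the investigator and Sponsor prior to administration"; the prior-use exception carries no such step.

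Section 8.1.5.2 adds: "The investigator will record medication used by participants during the study". A footnote to the Study Schedule (Section 1.3) fixes the earliest screening: "Screening test will be performed within 3 weeks prior to study drug administration". Of the Per-Protocol set, Section 9.2.3 says: "This set of participants will be included in the pharmacokinetic analysis".

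**The concern.** The recording period matches the general prohibition and stops 14 days short for the one class with a longer period. By giving inducers 28 days, the protocol treats use in the third and fourth weeks before dosing as potentially relevant to pharmacokinetics. Section 6.4 then lets such use be accepted on the investigator's judgement, without asking for the drug, dates or reasons to be written down.

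Taken together, a participant with recent inducer use could be dosed and counted in the PK analysis while the people who set the Per-Protocol set and read the Japanese/non-Japanese geometric mean ratio do not know of it. With about 12 participants, and a study that exists because Japanese PK data were a condition of approval (Section 2.1), one would want that history to be visible.

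**Working it through.** **Day count.** Inputs: prohibition Days -28 to -1 and recording Days -14 to -1 (8.1.5.1); consent and screening on Day -21 at the earliest (1.3).

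- Barred but not expressly recorded as prior medication: 28 - 14 = 14 days (Days -28 to -15).
- If use after consent counts as use during the study (8.1.5.2), the uncovered days are those in the range -28 to -15 that precede consent:

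| Consent | Uncovered days | Number |
|---|---|---|
| Day -21 | -28 to -22 | 7 |
| Day -18 | -28 to -19 | 10 |
| Day -14 or later | -28 to -15 | 14 |

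The gap is never zero.

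**Who can fall into it.** Inducer use in the last 14 days is recorded. That leaves a healthy man aged 20 to 45 who took an inducer, stopped between Days -28 and -15, told the site so at the washout review, and was accepted because the investigator could justify that it did not matter for the study. Nothing in the documents suggests that such a man is expected.

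**What else catches it.** Section 8 requires the investigator to keep details of everyone screened and the records that confirm eligibility; exclusion 7, with its 28-day limb, is one of the criteria to be confirmed. Section 8.1.11 checks at admission that medication requirements have been respected since screening. Section 10.2.7 gives monitors source review. None of these names the CRF or an inducer history, so they narrow the gap without closing it. Sections 5.4, 8.4.1 (Table 2) and 10.2.7 refer to data handling guidelines and data management procedures held separately; these were not available and may ask for more.

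**Size, by assumption only.** The documents give no residual induction effect. First, the plan's own precision (9.2.6): half-width = t(0.975, 11) × SD / √12.

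- AUC: 2.201 × 0.367 / 3.464 = 0.233 (plan: 0.233).
- C24hr: 2.201 × 0.590 / 3.464 = 0.375 (plan: 0.375).

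If one of 12 participants has exposure r times what it would have been, the log mean shifts by |ln r| / 12 and the geometric mean is multiplied by r^(1/12):

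| r | Log shift | Fall in geometric mean | Share of AUC half-width | Share of C24hr half-width |
|---|---|---|---|---|
| 0.8 | 0.0186 | 1.8% | 0.08 | 0.05 |
| 0.6 | 0.0426 | 4.2% | 0.18 | 0.11 |
| 0.4 | 0.0764 | 7.4% | 0.33 | 0.20 |

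The model in 9.2.4 has ethnicity as its only term, so the ratio moves by the same factor. Its 90% interval depends on the comparator numbers, which the plan does not fully give. The narrowest case is an unlimited comparator group with the same SD, with half-width 1.645 × SD / √12 = 0.174 for AUC and 0.280 for C24hr. On that yardstick the shares run from 0.0186/0.174 = 0.11 to 0.0764/0.174 = 0.44 for AUC, and from 0.07 to 0.27 for C24hr. Any real comparator group gives a wider interval and smaller shares.

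The lower rows should be discounted. A loss of 40% to 60% is hard to square with use that the investigator has justified as unimportant to a PK study.

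**The case for a change.** The best case for a change is that it would cost almost nothing. The site already asks about the 28 days, so recording the answer for inducers needs one sentence and a few CRF entries, and no eligibility rule moves. Section 6.4 makes the exception legitimate, so such a man need not be flagged as a deviation, and Section 9.2.3 requires reasons only for those excluded from analysis. A site eligibility file is not study data.

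Much of this stands as description. The text has no express duty to capture the use, and the site safeguards do not guarantee that an analyst sees it. One part is less certain: 8.1.5.1 itself bars inducers for 28 days without mentioning the 6.4 exception, so on a strict reading accepted use could still be considered as a deviation when the Per-Protocol set is defined.

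What does not follow is a consequence for the results. Being cheap is not a reason to change the plan when the change alters neither who is dosed nor any planned estimate. A prespecified analysis with and without such a participant would serve a hypothetical case in a comparison that is exploratory and tests no hypothesis (9.2.4, 9.2.5). If a case arose, Section 9.2 already provides for analysis changes to be documented with reasons in the study report.

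**Conclusion.** No change is needed. The 14-day and 28-day periods do not match, and between 7 and 14 days of possible inducer use have no express recording rule. That is a gap in documentation. Followed as written, the plan still reviews the whole 28-day washout, still applies exclusion 7, and admits prior inducer use only where it is judged not to matter for the study. The PK estimates are sound on those terms, and longer recording would add traceability without altering them.

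The conclusion assumes that investigators apply the washout review and the 6.4 judgement as written, and that accepted cases are rare, at most about one in 12. The exposure losses are assumed, not documented; even the largest moves the geometric mean by 7.4%, within the planned interval. The mismatch in the text is certain. Whether analysts would in practice lack the information is not, because the separate data handling documents were not available.
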